3. STUDY METHODS AND PROCEDURES

3.1 Study Treatment/Intervention

Patients assigned to the intervention group will undergo BFR exercises in addition to the standard rehabilitation protocol. BFR therapy will be administered at an INOVA physical therapy location by a certified physical therapist that is trained in BFR modalities. Therapists will follow a standardized ACL rehabilitation protocol (see appendix), which consists of 2-3 therapy sessions per week following surgery. BFR exercises will begin after the surgical incision has healed and post-operative swelling is minimized. This generally occurs two weeks post-operatively.

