3.4.2 Secondary Outcomes

The secondary objective is to determine if BFR exercises are associated with adverse effects such as numbness, tourniquet-site pain, and bruising.

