 - International Knee Documentation Committee Subjective Knee Evaluation Form (IKDC)
 - VAS
 - Completed at 3 month intervals
 - Baseline (prior to surgery)
 - 3 months, 6 months, 9 months, 12 months, 24 months
- Limb Symmetry Index (LSI)
 - Consists of 4 assessments:
 - Single hop for distance, triple hop for distance, cross-over hop for distance, 6 meter hop for time
 - Compare operative leg vs. non-operative leg
 - Completed at 3 month intervals after surgery
 - 3 months, 6 months, 9 months, 12 months
- Quadriceps muscle assessment
 - Thigh circumference
 - Compare operative leg vs. non-operative leg
 - Completed at 3 month intervals
 - Baseline (prior to surgery)
 - Just for thigh circumference
 - 3 months, 6 months, 9 months, 12 months
- Return to sport
 - Defined as the date that patient is cleared for return to all sports without restriction by their physician utilizing an objective return to play criteria.

Adverse Effects:

- Therapist-completed survey of BFR:
 - Administered during PT session
 - Assesses for bruising, tourniquet-site pain, numbness, compartment syndrome, rhabdomyolysis
- Miscellaneous complications:
 - Ie: DVT/PE, reinjury, return to operating room, etc.
 - Will be recorded during office visits

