7. ADVERSE EVENT REPORTING

Potential Adverse Event: Breach of Confidentiality.

Patient confidentiality will be maintained at all times. All records will be assigned a case number. Information collected in this study will be stored in a locked file cabinet in a secure office and will be accessible only to the research staff. Subject will not be identified in any publications or presentations of the research results.

All adverse events (AEs) will be reported and logged per the IRC 11.16 policy in the Inova Research Center Standard Operating Procedures manual.

In the event of an AE, defined as “Any untoward medical occurrence (including a symptom/disease or an abnormal laboratory finding) during treatment with a pharmaceutical product in a patient or a human volunteer that does not necessarily have a relationship with the treatment being given,” the research coordinator will immediately document and report all applicable details to the IRB via the “Reportable Event” form, including start and end date (if applicable), severity, therapy provided, and relationship to protocol. If the AE/SAE occurs at the lead site, the “Internal AE/SAE” form will be completed. If the AE/SAE occurs at a site other than the lead site, that site will notify the lead site immediately with the aforementioned applicable details, as well as follow their own institution’s protocol for AE reporting if applicable. The lead site coordinator will then submit the “External AE/SAE” form to the lead IRB.

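### The survey behind the BFR safety objective has no pre-cuff recording, no stated question about the time between sessions and no stated use in controls, so cuff effects cannot be reliably separated from post-surgical findings

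*Combined protocol and SAP*

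**What the plan says.** Section 3.4.2 sets the secondary objective: whether BFR exercises are associated with "adverse effects such as numbness, tourniquet-site pain, and bruising".

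Under Adverse Effects, section 3.6 lists a "Therapist-completed survey of BFR", described as "Administered during PT session". Its content is: "Assesses for bruising, tourniquet-site pain, numbness, compartment syndrome, rhabdomyolysis". The section does not say which sessions it applies to, when in the session it is filled in, what period it covers, or whether control patients receive it.

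On timing, section 3.1 states that "BFR exercises will begin after the surgical incision has healed and post-operative swelling is minimized", which it places at generally two weeks after the operation. Sections 3.1 and 3.2 give both arms 2-3 therapy sessions a week.

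There are two other routes for safety data. Section 3.6 has miscellaneous complications (clots, reinjury, return to the operating room and similar), of which it says: "Will be recorded during office visits". Section 7 says: "All adverse events (AEs) will be reported and logged per the IRC 11.16 policy".

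**The concern.** An association needs a reference: the patient's own state before the cuff, or patients who never have the cuff. As written, the survey is stated to have neither. Two of its items, numbness and bruising, are also findings that knee surgery can leave behind, and the survey begins soon after surgery.

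The period covered is also unstated. Some of the listed items may appear after the patient has left the session. If the therapist records only what is seen while the cuff is in use, they may not reach the form.

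At stake is whether the secondary objective can be interpreted. A percentage of BFR patients with numbness or bruising could be read as a harm of the cuff when part of it is post-operative, and a low count could be read as reassurance when the interval was never asked about. A pre-cuff state that was not recorded cannot be recovered later.

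**Working it through.** **Plan's own figure.** There is none for safety. The sample size statement in section 4.1 (150 patients, 80% power, alpha 0.05) concerns functional outcomes. It gives no difference, standard deviation or dropout rate, so it cannot be reproduced. This point does not depend on it.

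**Step 1: the text side by side.**

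- *Baseline.* Section 3.6 specifies a pre-surgery baseline for KOOS, IKDC, VAS and thigh circumference, and none for the safety items. A pre-surgery value would not serve here anyway, because the operation comes between it and the cuff. The useful moment is just before the first cuff use.
- *Condition for starting BFR.* It refers to incision healing and to swelling being reduced. It does not mention numbness or bruising.
- *Comparator.* The form is named for BFR, and neither section 3.6 nor section 3.2 gives it to controls.
- *Analysis.* Section 4.2 offers frequency distributions for categorical data. No between-arm safety comparison is described.
- *Backups.* The office-visit examples include none of the five survey items. The log in section 7 covers all adverse events, but defines one as occurring "during treatment with a pharmaceutical product in a patient or a human volunteer", which does not fit a cuff, and it prompts no specific question.

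**Step 2: how background mixes with cuff effects.** From the documents: 75 patients per arm (section 2.4) and two-sided alpha 0.05 (Abstract). Assumed: a share b = 5% to 30% of patients with the finding for reasons other than the cuff, and a cuff-caused rate e = 10% among the rest.

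Observed rate in BFR patients: p = b + (1 - b) × e. Share that is background: b / p.

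| b | p | b / p |
|---|---|---|
| 5% | 0.05 + 0.95 × 0.10 = 14.5% | 34% |
| 10% | 0.10 + 0.90 × 0.10 = 19% | 53% |
| 20% | 0.20 + 0.80 × 0.10 = 28% | 71% |
| 30% | 0.30 + 0.70 × 0.10 = 37% | 81% |

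A BFR-only survey shows the p column and has nothing from which to recover b.

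**Step 3: what surveying both arms would give.** With 75 per arm and no dropout, the difference is p - b. Its 95% half-width is 1.96 × √[(b(1-b) + p(1-p)) / 75]. Power uses the normal approximation with pooled variance under the null.

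| b | p - b | Half-width | Power |
|---|---|---|---|
| 5% | 9.5 points | 9.4 points | 50% |
| 10% | 9 points | 11.2 points | about 35% |
| 20% | 8 points | 13.6 points | 21% |
| 30% | 7 points | 15.1 points | 15% |

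The comparison becomes interpretable but stays imprecise. Excluding findings already present at the pre-cuff recording lowers b, which moves the trial towards the upper rows.

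**Step 4: what incomplete capture would cost.** Suppose a harm has a true rate of 5% and the survey captures a fraction c (both assumed). The chance of seeing at least one case in 75 is 1 - (1 - 0.05c)^75, which is 98%, 94%, 85% and 61% for c = 100%, 75%, 50% and 25%. With no events seen in 75 patients and full capture, the one-sided 95% upper bound is 1 - 0.05^(1/75) = 3.9%. At half capture the same result bounds the true rate only at 3.9% / 0.5 = 7.8%. The documents do not allow c to be estimated.

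**The case against.** The case on the other side is substantial, and it limits what can be claimed.

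- A reader might infer that the survey misses harms that appear after the session. The text does not show this. It says when the form is given, not what period it covers. Sessions recur 2-3 times a week, so a bruise may still be visible or be reported at the next one, and listing rhabdomyolysis and compartment syndrome is compatible with asking about the interval. The form itself is not in the documents. The share of the week spent in therapy is no measure of capture either, since a form can record events from outside the session.
- A reader might take the survey to be the only safety source. It is not. Office visits collect complications, and section 7 requires all adverse events to be logged with dates, severity and relationship to protocol. What stands is narrower: the survey is the only instrument that names the effects in the secondary objective.
- Tourniquet-site pain is tied to the cuff by name, the cuff sits proximally (section 1.3), and BFR waits for healing. This reduces the overlap with surgical findings. It does not remove it for numbness and bruising, for which no site or attribution rule is given.
- A reader might infer that the therapist has a stake in the result. Nothing in the documents supports that, and a therapist-completed form can still record the patient's answers.
- The randomised control arm could supply background rates. That is correct, but only if controls are surveyed, which is not stated.

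**Conclusion.** The point holds as a gap in measurement. Following section 3.6 as written, numbness and bruising already present about two weeks after surgery cannot be reliably separated from cuff effects, capture of later-onset effects is not assured, and no stated comparator lets the survey answer a question about association. The documents do not support saying that later harms will be missed, or that controls are excluded from the survey; both matters are unstated.

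The size is illustrative. The 34% to 81% background share rests wholly on the assumed 10% cuff-caused rate and 5% to 30% background. That some patients still have numbness or bruising when BFR starts is also an assumption, though a modest one.

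The functional outcomes are unaffected. The change is worth making because the secondary objective depends on it and the pre-cuff state cannot be reconstructed afterwards.

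**What to change.** Amend the Adverse Effects entry in section 3.6, and add one sentence to section 4.2:

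- (a) Record the survey items once before the first cuff use, and at the matching session (about week 2) in control patients.
- (b) At the start of each session, ask the patient about the time since the last session and note the date of onset. Keep the existing in-session check.
- (c) Use the common items (numbness, bruising and thigh pain) in both arms. Thigh pain stands in for tourniquet-site pain, which has no meaning without a cuff.
- (d) Count new or worsened findings and compare them between arms. Given the precision in step 3, report the difference with its confidence interval and do not read a non-significant test as evidence of safety.

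The cost is about a minute per session in both arms (an estimate), at sessions that already take place, with no new visits or staff. One limit remains: no sham cuff is described, so patients will know their arm and symptom reports may reflect that.

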4. STATISTICAL CONSIDERATIONS/DATA ANALYSIS

4.1 Sample Size

We are currently aware of no studies that use KOOS, IKCD scores, limb symmetry index, or return to play for BFR therapy after ACL reconstruction. However, studies [10, 11, 12, 13] of similar populations have found OOS, IKDC, LSI, RTP values of 91.5, 87.5, 79%, and 209 days, respectively. Using those estimates, a power analysis was done and sample size of 150 provides enough power (80%, with an alpha of 0.05) to detect clinically significant changes in these values, while simultaneously accounting for any potential loss-to-follow-up or early withdrawal from the study.

4.2 Method of Data Analysis

Descriptive statistics including measures of location (mean, median, percentile) and spread (standard deviation, ranges) will be computed for continuous variables. Frequency distributions will be computed for categorical data. Measures of association will be used to determine positive and negative predictors of functional outcomes and return to sport.

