Outcome measures will include Knee Injury and Osteoarthritis Outcome Score (KOOS), International Knee Documentation Committee Subjective Knee Evaluation Form (IKDC), Limb Symmetry Index (LSI), thigh circumference, and return to sport. Baseline scores will be obtained prior to surgery when applicable. Outcomes will be measured at designated time intervals for 2 year following surgery.

Statistical Methodology: Data will be reviewed by a trained statistician. Repeated-measures analysis of variance (ANOVA) will be used to evaluate all patient-reported outcome surveys at multiple time points. All statistical tests will use two-tailed hypothesis testing with the statistical significance a priori set at alpha, α , is equal to 0.05

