2.4 Number of Subjects

The goal is to include 150 subjects in the study, which will be divided into 75 patients in the treatment group and 75 patients in the control group.

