3.6 Data Collection

The following data will be recorded:

Demographics:

- Gender
- Age at time of surgery
- BMI at time of surgery
- Sports participation (if applicable):
 - Type of sport
 - ie: football, soccer, baseball, track, etc.
 - Level of competition
 - High school
 - Collegiate

- Professional
 - Recreational
- Prior knee injuries:
 - Eg. ipsilateral/contralateral ACL tears, meniscal injuries, chondral injury
- Smoking status
 - Non-smoker
 - Former smoker
 - Smoker (number of packs per day)
- Diabetes

Injury Data:

- Laterality of injury
 - Left
 - Right
- Date of injury
- Time from injury to surgery
- Mechanism of injury:
 - Contact
 - Non-contact (ie: twisting)
- Concomitant ligament injury observed on MRI:
 - Ligament
 - Medial Collateral Ligament (MCL)
 - Lateral Collateral Ligament and/or Posterolateral corner (LCL/PLC)
 - Posterior Cruciate Ligament (PCL)
 - Severity of injury
 - Grade 1: (minor sprain) high signal is seen medial (superficial) to the ligament, which looks normal
 - Grade 2: (severe sprain or partial tear) high signal is seen medial to the ligament, with high signal or partial disruption of the ligament
 - Grade 3: complete disruption of the ligament
 - Note: Concomitant ligament injury *requiring reconstruction* is an exclusion criteria

Intraoperative Data:

- Type of ACL graft:
 - Bone-patellar tendon bone (BTB) autograft
 - Hamstring tendon (HS) autograft
 - Allograft
- ACL graft fixation (interference screws, suspensory fixation)
- Concomitant injuries observed intraoperatively
 - Meniscal tear
 - Medial vs. Lateral
 - Type of tear (longitudinal, radial, degenerative, bucket-handle)
 - Chondral injury
 - Location
 - Medial compartment
 - Lateral compartment
 - Patellofemoral joint
 - Severity (Outerbridge Classification)
 - Grade 0: normal
 - Grade I: cartilage with softening and swelling

- Grade II: partial-thickness defect with fissures on the surface that do not reach subchondral bone or exceed 1.5 cm in diameter
 - Grade III: fissuring to the level of subchondral bone in an area with a diameter more than 1.5 cm
 - Grade IV: exposed subchondral bone
- Concomitant procedures performed:
 - Meniscectomy
 - Partial vs. Complete
 - Medial vs. Lateral
 - Meniscal repair
 - Chondroplasty
 - Microfracture
 - Note: Concomitant procedure requiring delayed weightbearing is an exclusion criteria

Outcome Data:

- Validated patient reported outcomes:
 - Surveys:
 - Knee Injury and Osteoarthritis Outcome Score (KOOS)

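### Section 4.2 names no between-arm model for LSI, thigh circumference or return to sport, so the pre-surgery thigh value and other pre-treatment factors already collected enter no arm comparison

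*Combined protocol and SAP*

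**What the plan says.** Section 1.2 hypothesises a better result with blood flow restriction on LSI, thigh circumference and return to sport, among others. Section 3.4.1 lists LSI and return to sport as primary outcomes; thigh circumference is not on that list.

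The Abstract (Statistical Methodology) names repeated-measures ANOVA, for the patient-reported surveys only, and sets the general rule "All statistical tests will use two-tailed hypothesis testing with the statistical significance a priori set at alpha" at 0.05. Section 4.2 then covers everything else. Continuous data: "Descriptive statistics including measures of location (mean, median, percentile) and spread (standard deviation, ranges) will be computed for continuous variables". Categorical data get frequency distributions. Finally: "Measures of association will be used to determine positive and negative predictors of functional outcomes and return to sport". The candidate predictors are not listed, and the section does not say whether study arm would be in those models.

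Section 3.6 sets out what is available. Thigh circumference is measured before surgery (the baseline entry under the quadriceps assessment reads "Just for thigh circumference") and at 3, 6, 9 and 12 months, operative against non-operative leg. LSI is measured at the same four post-operative visits, with no pre-surgery value. KOOS, IKDC and VAS have a pre-surgery score. Age, gender, BMI, sport and level of competition, prior knee injury, smoking, diabetes and time from injury to surgery are recorded. "Type of ACL graft" is recorded too, but under intraoperative data. Return to sport is defined as a date of physician clearance.

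**The concern.** Three outcomes carry directional hypotheses, two of them are primary, and none has a stated method for comparing the arms. An analyst following Section 4.2 literally would report means and SDs by arm and then look for predictors. Information recorded before treatment that could sharpen the arm comparison would play no part in it.

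This matters more here because Section 3.3 describes assignment by a random number generator with no stratification, in a population aged 13 to 55 that ranges from recreational to professional athletes. The design does nothing to balance the arms on such factors, so adjustment in the analysis is the remaining way to recover that precision. Prespecification matters as well. If covariates are picked after the predictor search has been run, the adjusted arm comparison becomes data-driven.

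**Working it through.** **Inputs from the documents.** Two-sided alpha 0.05 (Abstract; Section 4.1); 80% power (Section 4.1); "75 patients in the treatment group and 75 patients in the control group" (Section 2.4).

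**Inputs the documents do not give.** No target difference, SD or loss rate is stated for any outcome, and no correlation between baseline and follow-up. Section 4.1 gives one reference level each for KOOS, IKDC, LSI (79%) and return to play (209 days), and none for thigh circumference. The assumed ranges below are the share of outcome variance explained, R² = 0.05 to 0.25, and the baseline correlation for thigh circumference, r = 0.3 to 0.7 (so R² = r²).

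**Step 1: the plan's own figure.** Section 4.1 says that "a power analysis was done and sample size of 150 provides enough power (80%, with an alpha of 0.05) to detect clinically significant changes". This cannot be rebuilt, because a difference and an SD are missing. It can only be solved backwards:

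d = (1.960 + 0.842) × √(2/75) = 2.802 × 0.1633 = 0.457 SD (normal approximation); the two-sample t-test gives 0.4605. So 75 per arm with no loss has 80% power for about 0.46 SD.

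**Step 2: effect of adjustment on a mean outcome.** Adjustment multiplies the residual variance by (1 − R²), so

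power ≈ Φ(2.802/√(1 − R²) − 1.960), and the equivalent unadjusted sample size is 150/(1 − R²).

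| Assumption | R² | 2.802/√(1 − R²) | Power | Equivalent N |
|---|---|---|---|---|
| No adjustment | 0 | 2.802 | 80.0% | 150 |
| Prognostic factors, low | 0.05 | 2.874 | 82.0% | 158 |
| Prognostic factors, middle | 0.10 | 2.953 | 84.0% | 167 |
| Prognostic factors, high | 0.25 | 3.235 | 89.9% | 200 |
| Thigh baseline, r = 0.3 | 0.09 | 2.937 | 83.6% | 165 |
| Thigh baseline, r = 0.5 | 0.25 | 3.235 | 89.9% | 200 |
| Thigh baseline, r = 0.7 | 0.49 | 3.923 | 97.5% | 294 |

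The t-distribution gives the same powers to within 0.1 percentage point. The gain depends on the starting power and on R², and hardly at all on how many completers that starting power refers to. The thigh rows borrow the 80% start, since Section 4.1 makes no power claim for that outcome.

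**Step 3: return to sport.** The variance formula is for means and gives no figure for a time-to-event outcome. Covariate adjustment of a hazard ratio tends to raise power rather than narrow the interval, and it changes the quantity estimated to a conditional one.

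**Step 4: which factors are eligible.** Section 3.3 randomises at enrolment, before surgery. Graft type, meniscal findings and concomitant procedures are intraoperative records, so they follow randomisation, and no blinding of the surgeon is described. Age, sex, prior knee injury and level of competition are fixed beforehand. The pre-surgery IKDC and thigh values precede treatment, which starts about two weeks after surgery (Section 3.1), though the documents do not say whether they are taken before or after assignment.

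**The case against.** The strongest reply is that an unadjusted comparison of randomised arms is valid: chance imbalance is already allowed for in the standard error and the type I error rate. That stands. Adjustment here is an efficiency gain, and a reader who infers that raw arm differences would be biased goes beyond what the design supports.

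A second reply is that the plan has not chosen an unadjusted test; it has chosen no test. That also stands. It is tempting to read Section 4.2 as a decision to compare raw means, but the section contains no arm comparison for these outcomes, and it does not say how the clearance date would be summarised. Likewise, that the collected factors serve only the predictor search is a fair inference, not a statement in the plan.

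Third, the gains may be smaller than the upper figures. LSI and thigh circumference are both operative-versus-non-operative comparisons, which may already remove much of the variation due to age, sex and body size. The lower rows of the table are therefore as plausible as the upper ones.

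Fourth, a reader might keep 0.46 SD as the target, suppose 64 completers per arm (about 15% loss) and conclude that unadjusted power falls to 73%. Section 4.1 does not support this, since it says its 80% already allows for loss. On that reading 64 completers would have 80% power, at 0.50 SD, and a full 75 would have 86%. Neither reading can be verified.

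Finally, graft type may look like a covariate already in hand. It is not a pre-randomisation one: using planned graft would need a field that Section 3.6 does not contain.

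**Conclusion.** The point holds as a gap in Section 4.2 with a cheap remedy, and the plan should be changed. LSI, thigh circumference and return to sport have no between-arm model, and the data that could make such a model more precise are collected without being assigned to one. What is lost is precision, not validity.

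The size is conditional. From 80% power at 75 per arm, it is about 82% to 90% for R² of 5% to 25%, and about 84% to 98% for a thigh baseline correlation of 0.3 to 0.7. Both ranges are assumptions, and so is the 80% start for thigh circumference. The baseline argument applies directly only to thigh circumference, which is not a listed primary outcome; LSI can gain only from prognostic factors, probably modestly. No numerical gain is claimed for return to sport.

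**What to change.** In Section 4.2, name the arm comparison for each outcome:

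- **Thigh circumference:** a longitudinal model over 3, 6, 9 and 12 months, with the pre-surgery value as covariate on the same operative-versus-non-operative scale as the outcome.
- **LSI:** a longitudinal model over the same visits, adjusted for a short prespecified list already collected: age, sex, prior knee injury and pre-surgery IKDC.
- **Return to sport:** a time-to-clearance model, with censoring defined, adjusted for age and level of competition. Report the unadjusted result alongside, because the adjusted hazard ratio is a conditional estimand.

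State that baseline measurements used as covariates are taken before assignment. Leave out graft type and other intraoperative data unless planned graft is recorded before randomisation. Surgeon (Section 3.5 indicates two) is an optional covariate and would also need a new field. Keep the predictor search separate and label it exploratory.

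Cost: SAP wording, settled before any outcome data are compared by arm. No extra patients or visits, and no new data field unless planned graft or surgeon is wanted, at one field each.
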